5.2 Primary variable(s)

The 3 primary efficacy variables will be lesion visualization parameters based on a blinded read (see Section 10.2.1.5 for details):

- Degree of lesion contrast enhancement
- Lesion border delineation
- Lesion internal morphology

5.3 Secondary efficacy variables

The secondary efficacy variables are the:

- Number of lesions identified (up to 10) based on a blinded read
- Identification of benign or malignant disease based on blinded read
- Confidence in diagnosis based on a blinded read
- Image quality based on a blinded read
- Contrast enhancement utilizing an exploratory Overall Contrast Enhancement Estimation Algorithm.

5.4 Justification of the design

Gadoterate is an approved macrocyclic contrast agent for steady-state CNS imaging. It has the lowest relaxivity among all approved gadolinium contrast agents and was therefore chosen as the comparator. Gadoterate belongs to the same chemical class as gadobutrol, which is also a macrocyclic contrast agent. Macrocyclic contrast agents may be considered preferable to linear agents in certain situations, for example, in light of Nephrogenic Systemic Fibrosis (NSF), which has been rarely observed in renally impaired patients who received multiple and/or high doses of primarily linear GBCAs, and in the accumulation of gadolinium in tissues, also thought to occur to a lesser extent with macrocyclic agents. In addition, as both of these conditions appear to be dose-related, the lowest dose of gadolinium is recommended.

26 MAR 2019 Version no. 2.0 Page: 16 of 60

The purpose of this study is to demonstrate that the higher relaxivity of gadobutrol compared to gadoterate will permit a dose reduction by 25% for gadobutrol and still provide noninferior efficacy to a full dose of gadoterate.

The patient population for this study will be those with known or highly suspected lesions of the CNS referred for a contrast-enhanced MRI of the CNS.

The multicenter design is used to gain a wide range of experience and to reduce bias.

A prospective planned blinded image evaluation by independent readers will be performed in order to facilitate an independent evaluation and permit randomization of the image evaluation. The blinded readers will be experienced radiologists who will not have been involved in the clinical portion of the study and are considered independent from the study. Selecting experienced readers and performing adequate and extensive reader training prior to the evaluation of the images is expected to sufficiently address standardization issues and to minimize inter-reader variability. All quantitative measurements and qualitative evaluations of the MRI data will be performed in a core laboratory in a standardized fashion using validated software.

5.5 End of study

The end of the patients' participation in the study will be reached at the last patient last visit, defined as when the final clinical diagnosis is obtained for the last patient enrolled. The end of the study will be considered the end of the blinded read, approximately 30 days after the LPLV.

5.6 Primary objectives

The primary objective of this study is to demonstrate noninferiority of gadobutrol-enhanced CNS imaging (at a three-quarter dose of 0.075 mmol/kg) compared to gadoterate -enhanced CNS imaging (at a full dose of 0.1 mmol/kg) for 3 lesion visualization parameters (degree of enhancement, border delineation, internal morphology) based on a blinded read.

5.7 Primary completion

The primary completion event for this study is completion of the blinded read for all patients.

The primary completion date for this study according to the FDA Amendment Act is specified in a separate document (not part of this study protocol).

6. Study population

6.1 Eligibility

Male and female patients (\geq 18 years of age) of any ethnic group, who meet the inclusion criteria and none of the exclusion criteria, and who give written informed consent will be eligible for enrollment into the study.

26 MAR 2019 Version no. 2.0 Page: 17 of 60

6.2 Inclusion criteria

To be included in the study a patient must:

- 1. Have known or highly suspected CNS pathology referred for contrast-enhanced MRI of the CNS based on current clinical symptoms or on a previous procedure.
- 2. If female and of child bearing potential, have a negative urine pregnancy test within 1 hour prior to the administration of gadoterate (the first MRI).
- 3. Have an estimated glomerular filtration rate (eGFR) value \geq 60 mL/min/1.73m² derived from a serum creatinine result within four (4) weeks prior to the first study MRI.
- 4. Be fully informed about the study, including provisions of the Health Insurance Portability and Accountability Act (HIPAA) as applicable, and consent to participate

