5.1 Design overview

This study is a Phase 4, multicenter, controlled, cross-over study with corresponding blinded image evaluations in male and female patients at least 18 years of age, who are referred for a contrast-enhanced MRI of the CNS based on a known or highly suspected lesion of the CNS.

Patients will undergo an unenhanced and contrast-enhanced MRI of the CNS using gadoterate at the standard dose of 0.1 mmol/kg BW. If the investigator does not identify an enhancing lesion of the CNS, then this patient will be considered a screening failure. If an enhancing lesion is identified, then the patient will undergo a second unenhanced and contrast-enhanced MRI of the CNS using gadobutrol at a dose of 0.075 mmol/kg BW.

Safety will be assessed from the first administration of gadoterate through 24 hours after the second administration of gadobutrol. Adverse events will be collected from the signing of informed consent through the end of the follow-up period. Serious adverse events (SAEs) will be followed through resolution. Patients who receive only the first MRI scan (considered screening failures) will be followed for SAEs only.

Gadobutrol will be administered at the dose of 0.075 mmol/kg body weight by single IV injection at a rate of 2 mL/sec, followed by 20-mL 0.9% saline flush at the same rate. Gadoterate will be administered at the approved standard dose of 0.1 mmol/kg body weight by single IV injection at 2 mL/sec, followed by 20-mL 0.9% saline flush at the same rate. The 2 injections will be separated by at least 24 hours, but not more than 15 days.

During the course of the study, 2 MRIs will be obtained from each patient as follows: before the administration of each of the contrast agent (unenhanced MRI) consisting of steady-state sequences (T1w, T2w, and FLAIR), following the gadoterate injection (gadoterate-enhanced MRI) consisting of steady-state sequences T1; and following the gadobutrol injection (gadobutrol-enhanced MRI) consisting of steady-state sequences (T1w).

The unenhanced MR image set, combined unenhanced and gadobutrol-enhanced MR image sets, and the unenhanced and combined unenhanced and gadoterate-enhanced MR image sets will be evaluated by 3 independent blinded readers. The blinded readers will also evaluate the

26 MAR 2019 Version no. 2.0 Page: 15 of 60

gadobutrol-enhanced T1w images compared to the gadoterate-enhanced T1w images in a paired read for image quality.

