6.3 Exclusion criteria

A patient will be excluded from the study if he/she:

- 1. Has no enhancing lesion visible on the gadoterate-enhanced MRI scan.
- 2. Is pregnant or breast feeding
- 3. Has received any investigational product or has participated in any other clinical trial within 30 days prior to enrolling in this study
- 4. Has any contraindication to the MRI examinations or the use of gadolinium-containing contrast agents
- 5. Has a history of severe allergic or anaphylactic/anaphylactoid reaction to any allergen including drugs and contrast agents
- 6. Has received any gadolinium-based contrast agent < 24 hours prior to the study MRIs, or is scheduled to receive any contrast agent within 24 hours after the second study MRI
- 7. Is considered clinically unstable
- 8. Has severe cardiovascular disease (eg, known long QT syndrome, acute myocardial infarction [< 14 days], unstable angina, congestive heart failure New York Heart Association class IV or acute stroke (< 48 hours)
- 9. Is expected or is scheduled to have a change in any treatment or procedure between the gadoterate and gadobutrol MRIs that may alter image comparability
- 10. Is scheduled or is likely to require a biopsy or any interventional therapeutic procedure from the first study MRI up to 24 hours after the second study MRI

26 MAR 2019 Version no. 2.0 Page: 18 of 60

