9.1 Tabular schedule of evaluations

Table 9-1 displays the schedule of evaluations and procedures for the study.

26 MAR 2019 Version no. 2.0 Page: 24 of 60

Table 9-1: Schedule of Study Events

		Stu	udy Period 1 ^a			Stud	dy Period 2 ^a		
Evaluation/Procedure	Baseline ^b	MR	I	Post Injection Phone Contact ^c	Baseline ^C	MR	I	Post Injection Phone Contact ^c	Final Diagnosis up to 30 days Phone call
Time Point	Up to 72 hours prior to the 1st MRI	Unenhanced	Enhanced	24h±4h	Within 24 h of the 2 nd MRI	Unenhanced	Enhanced	24h (±4 h)	Thorne can
Sign informed consent	Х								
Demographic data	X								
Medical/surgical history	X								
Baseline findings	X								
Referral diagnosis	X								
Previous/concomitant medications ^d	X			X	×			Х	
Weight ^e	χi				χi				
Urine pregnancy test ^f	χi								
Creatinine value ^g	X								
Gadoterate administration			Х						
Gadobutrol administration							Х		
Adverse event monitoring	X	Х	Х	Х	Х	Х	Х	Х	
Final clinical diagnosis up to 30 day post first MRI ^h									Х

Clinical Study Protocol

No. BAY No. 86-4875/ IMPACT no. 19773

26 MAR 2019 Version no. 2.0 Page: 25 of 60

Abbreviations: h = hour(s); immed = immediately; inj = injection; min = minutes

Notes:

- ^a A period of 24 h up to 15 days is required between the contrast agent injections;
- b Baseline for study period 1 is from after signing informed consent up to 72 hours for gadoterate administration;
- ^c Baseline for study period 2 is within the 24 h prior to administration of gadobutrol. At least 2 h is required between the 24-h follow-up evaluations from study period 1 and the baseline evaluations for study period 2. The patient will be contacted by phone after 24-hour (± 4 hours) after each contrast agent injection. The two MRI contrast agents will be separated by at least 24 hours, but not more than 15 days. Any TEAEs or TESAEs and/or concomitant medications reported during this period will be recorded in the eCRF.
- d All concomitant medication will be collected
- ^e Weight will be obtained at baseline and reconfirmed prior to the second MRI
- f Urine pregnancy test (if applicable) to be done at the site, according to the standard of the institution, and the results must be available prior to the gadoterate MRI.
- g Serum creatinine (eGFR value calculated using either MDRD or the CKD-EPI Creatinine Equation, 2009) derived up to 4 weeks prior to the first study MRI value and date obtained and method used needs to be recorded at Screening.

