- ^h The final clinical diagnosis will be recorded by the investigator within 30 days of the first study MRI.
- i Within 1h of injection

26 MAR 2019 Version no. 2.0 Page: 26 of 60

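### The urine pregnancy test is scheduled once, before gadoterate, and is not repeated before gadobutrol, so the result is 24 to 361 hours old at the second injection

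*Protocol*

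**What the plan says.** Protocol 6.2, criterion 2, requires a woman of child-bearing potential to "have a negative urine pregnancy test within 1 hour prior to the administration of gadoterate (the first MRI". In Table 9-1 the test appears once, in the baseline column of study period 1. Footnote f adds that "the results must be available prior to the gadoterate MRI", and footnote i sets the timing: "Within 1h of injection". SAP Table 3-1 has the same single entry and equivalent footnotes.

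The order of agents is fixed: section 7.2 states that it is not randomised, and section 9.2.2 puts gadoterate in period 1 and gadobutrol in period 2. On the interval, section 5.1 says: "The 2 injections will be separated by at least 24 hours, but not more than 15 days".

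Before gadobutrol, section 9.2.3 asks for changes in concomitant disease and medication and for placement of the IV line. Section 9.2.4 lists the imaging, the injection and a question about physical condition. Neither mentions a pregnancy test. Weight is handled differently: "Weight will be obtained at baseline and reconfirmed prior to the second MRI", with note i attached at both baselines.

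Exclusion criterion 2 (Protocol 6.3) bars a patient who "Is pregnant or breast feeding". It names no time point.

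**The concern.** The protocol sets its own standard for how recent a negative result must be before contrast is given: one hour. It applies that standard to the first injection only. Patients come to the study because they were referred for one contrast-enhanced MRI (sections 5.1 and 6.5). The second injection exists because of the cross-over comparison, so protecting the patient at that injection is the study's responsibility.

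A woman who conceived shortly before the first test, or between the two scans, could test negative at entry and be detectably pregnant at the second visit. A site that followed the schedule to the letter would inject gadobutrol on the strength of the old result. What is at stake is patient safety in a small group, not the validity of the efficacy comparison.

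**Working it through.** The plan states no figure for the age of the result, so there is none to reproduce. The check is interval arithmetic followed by a search for any text that orders a second test.

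**Inputs**
- Time from test to gadoterate: 0 to 1 h (Protocol 6.2, criterion 2; Table 9-1, note i).
- Time from gadoterate to gadobutrol: 24 h to 15 × 24 = 360 h (Protocol 5.1; Table 9-1, note a).
- Phone contact after gadoterate: 24 ± 4 h (Protocol 9.2.5).
- Table 9-1, note c: "At least 2 h is required between the 24-h follow-up evaluations from study period 1 and the baseline evaluations for study period 2".

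**Age of the result at gadobutrol** = (gadoterate to gadobutrol) + (test to gadoterate)
- Minimum: 24 + 0 = 24 h.
- Maximum: 360 + 1 = 361 h, or 361 / 24 = 15.04 days.

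**Is the 24 h minimum reachable under note c?**
- Call at 20 h: second baseline possible from 20 + 2 = 22 h, so the 24 h injection gap governs.
- Call at 24 h: second baseline from 26 h, so gadobutrol at 26 h at the earliest.
- Call at 28 h: second baseline from 30 h, so gadobutrol at 30 h at the earliest.

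The minimum of 24 h can be reached with an early call, and the range of 24 to 361 h stands.

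**Does any other text order a repeat?**
- Section 9.2.1 says that the result must be negative before any contrast agent is given. The sentence stands under the first baseline and refers to the one test described there. It schedules nothing for period 2.
- Section 7.2 makes the second MRI conditional on eligibility but orders no new test.
- The phone contact (9.2.5) collects adverse events and medication. Section 9.2.3 collects changes in disease and medication. Neither would detect a pregnancy of which the patient is unaware.

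**Result.** A scheduled test precedes one of the two injections. With a repeat within 1 hour before gadobutrol, the result would be 0 to 1 h old at both.

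**The case against.** The strongest reply is that the plan already protects against giving gadobutrol to a woman known to be pregnant. Exclusion criterion 2 has no time limit, section 7.2 ties the second scan to eligibility, and section 6.6.1 lets the investigator withdraw a patient for whom continuing would be harmful. This stands, and it narrows the gap to a pregnancy that nobody has recognised.

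A second reply is that weight is a poor comparator. It is repeated because the dose depends on it (Appendices 1 and 2). Serum creatinine, the other laboratory entry check, is also done once and may be four weeks old at the first MRI. This is fair: a single entry test is not peculiar to pregnancy in this protocol. But creatinine has a four-week window by design, whereas the protocol gave the pregnancy test a one-hour window and then did not apply it to the second injection.

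A third reply is that the risk is not quantified. That is also true. The documents give neither the number of women of child-bearing potential, nor a pregnancy rate, nor the distribution of intervals between scans. 361 h is the extreme, and a repeat after 24 h would add less than one after 15 days. A rule triggered only beyond a stated gap would be defensible, but the documents supply no basis for choosing the gap, and a uniform rule is simpler to run.

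A reader might also infer that a patient stopped between the scans would lose her non-serious gadoterate events, because section 5.1 says: "Patients who receive only the first MRI scan (considered screening failures) will be followed for SAEs only". The documents do not support this. Section 5.1 introduces screening failures as patients in whom no enhancing lesion is found, and section 9.2.2, item 3, ties the SAE-only rule to that case. Section 6.6.1 defines a dropout category for patients who stop after the first MRI. Its requirement that all eligibility criteria be met could be argued over for a newly pregnant patient, but her place in the safety set does not depend on that label: SAP 4.2 and SAP section 5 keep enrolled non-completers in it. SAP 6.1.1 already has a disposition row for stopping between the periods. No new classification rule is needed.

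**Conclusion.** The point holds as a minor, cheap patient-safety improvement. One urine test is scheduled, and its result is between 24 and 361 hours old when gadobutrol is injected. The exposure is confined to women of child-bearing potential with a pregnancy that was undetectable at the first test and is unrecognised at the second visit. No case count can be given, and none is claimed.

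The conclusion rests on two readings: that the sentence in section 9.2.1 about any contrast agent refers to the single first-baseline test, and that sites follow the schedule as written. If the sponsor meant that sentence to cover both injections, the schedule does not carry it out, and the same amendment is needed.

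Nothing here bears on the endpoints, the significance level, the power or the primary analysis. Section 6.6.2 continues recruitment until at least 180 patients have completed both scans, so an occasional patient stopped before gadobutrol does not erode the sample size.

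**What to change.** 1. Protocol 6.2, criterion 2: for women of child-bearing potential, require a negative urine pregnancy test within 1 hour before each contrast agent administration, naming both gadoterate and gadobutrol.
2. Table 9-1 and SAP Table 3-1: mark the test at the second baseline with note i, and extend footnote f to the gadobutrol MRI.
3. Protocol 9.2.3: add the test, with date, time and result entered in the eCRF as in section 9.2.1, and state that gadobutrol is not given if the result is positive.

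The cost is one extra urine test, of a kind the study already uses, for some patients at an existing visit, together with a short amendment and the added eCRF fields. The analysis sets and the disposition rules can stay as they are.

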6.3 Exclusion criteria

A patient will be excluded from the study if he/she:

- 1. Has no enhancing lesion visible on the gadoterate-enhanced MRI scan.
- 2. Is pregnant or breast feeding
- 3. Has received any investigational product or has participated in any other clinical trial within 30 days prior to enrolling in this study
- 4. Has any contraindication to the MRI examinations or the use of gadolinium-containing contrast agents
- 5. Has a history of severe allergic or anaphylactic/anaphylactoid reaction to any allergen including drugs and contrast agents
- 6. Has received any gadolinium-based contrast agent < 24 hours prior to the study MRIs, or is scheduled to receive any contrast agent within 24 hours after the second study MRI
- 7. Is considered clinically unstable
- 8. Has severe cardiovascular disease (eg, known long QT syndrome, acute myocardial infarction [< 14 days], unstable angina, congestive heart failure New York Heart Association class IV or acute stroke (< 48 hours)
- 9. Is expected or is scheduled to have a change in any treatment or procedure between the gadoterate and gadobutrol MRIs that may alter image comparability
- 10. Is scheduled or is likely to require a biopsy or any interventional therapeutic procedure from the first study MRI up to 24 hours after the second study MRI

26 MAR 2019 Version no. 2.0 Page: 18 of 60

6.4 Justification of selection criteria

The following is the FDA class warning for gadolinium-based contrast agents:

WARNING: NEPHROGENIC SYSTEMIC FIBROSIS

Gadolinium-based contrast agents increase the risk for Nephrogenic Systemic Fibrosis (NSF) in patients with: acute or chronic severe renal insufficiency (glomerular filtration rate < 30 mL/min/1.73m²), or acute renal insufficiency of any severity due to hepato-renal syndrome or in the perioperative liver transplantation period.

In these patients, avoid use of gadolinium-based contrast agents unless the diagnostic information is essential and not available with non-contrast-enhanced MRI. NSF may result in fatal or debilitating systemic fibrosis affecting the skin, muscle and internal organs. Screen all patients for renal dysfunction by obtaining a history and/or laboratory tests.

When administering a gadolinium-based contrast agent, do not exceed the recommended dose and allow a sufficient period of time for elimination of the agent from the body prior to any readministration.

It must be ensured that each patient is suitable for the technical requirements of a MRI examination, and especially that each patient has no metallic implants that would be affected by magnetic fields (Exclusion criterion 4).

In order to prevent interference with the investigational product and to ensure that the cause of TEAEs can be easily traced, no other contrast agents are to be administered (Exclusion criteria 6 and 7).

The physical condition of each patient must be stable and must not be significantly influenced by other therapies so that the patient does not have the potential for demonstrating unrelated TEAEs after contrast agent administration (Exclusion criterion 6).

To ensure that the patient's clinical picture is the same during gadobutrol-enhanced MRI and the gadoterate-enhanced MRI and there is no change due to external influences, no local or systemic therapy or biopsy/interventional therapeutic procedure should occur between the 2 MRI examinations (Exclusion criteria 10 and 11).

6.5 Recruitment

Patient recruitment will be from the patient populations at the investigative study centers who are referred for a contrast-enhanced CNS MRI.

26 MAR 2019 Version no. 2.0 Page: 19 of 60

6.6 Withdrawal of patients from study

6.6.1 Withdrawal

Withdrawal criteria

Patients *must* be withdrawn from the study if any of the following occurs:

• At their own request or at the request of their legally acceptable representative. At any time during the study and without giving reasons, a patient may decline to participate further. The patient will not suffer any disadvantage as a result.

Patients *may* be withdrawn from the study if any of the following occurs:

- If, in the investigator's opinion, continuation of the study would be harmful to the patient's well-being
- At the specific request of the sponsor and in liaison with the investigator (e.g. obvious non-compliance, safety concerns).

Depending on the time point of withdrawal, a withdrawn patient is referred to as either "screening failure" or "dropout" as specified in the following:

Screening failure

A patient who for any reason (e.g. failure to satisfy the inclusion/exclusion criteria), terminates the study before the time point used for the definition of "dropout" (see below) is regarded a "screening failure".

Dropout

A patient who satisfies all eligibility criteria, and discontinues study participation prior to the second MRI not due to an adverse event is defined as a "dropout" if the patient has already been submitted to the first study MRI.

General procedures

In all cases, the reason for withdrawal must be recorded in the CRF and in the patient's medical records.

The patient may object to the generation and processing of post-withdrawal data as specified in Section 13.4.

Any patient removed from the trial will remain under medical supervision until discharge or transfer is medically acceptable.

Details for the premature termination of the study as a whole (or components thereof) are provided in Section 13.

26 MAR 2019 Version no. 2.0 Page: 20 of 60

